#### **Transfusion-Free Hemoglobin**

A subject will be considered to have achieved transfusion-free hemoglobin normalization (TFHN) if the subject meets all of the following criteria:

- 1. Has two post-baseline measurements of hemoglobin at least 4 weeks apart that are both above the age-adjusted lower limit of normal (LLN);
- 2. Has no known additional measurements of hemoglobin that are below the age-adjusted LLN during the (minimum) 4-week period; and
- 3. Had no transfusions during the (minimum) 4-week period, and also no transfusions for 2 weeks prior to the first hemoglobin measurement in the (minimum) 4-week period.

If all 3 criteria are met, the subject will be considered to have achieved TFHN on the date of the first hemoglobin assessment in the 4-week period. The proportion of subjects who achieve TFHN will be summarized and, if sufficient data are available, a summary of time to TFHN will be created.

A subject who is transfusion-free beginning at Week 6 will be considered to have maintained transfusion-free normal hemoglobin if:

• regardless of baseline hemoglobin value, the subject has no abnormally low hemoglobin values beginning at Week 8 of the study and continuing for at least 13 weeks (3 months).

The proportion of subjects who have maintained transfusion-free normal hemoglobin will be summarized.

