Summary of planned clinical study be compared to rates/times reported in the literature, and will be discussed in conjunction with information derived from previous studies. Anthropometric indicators of growth, standardized by age and gender in accordance with the methodology described by the WHO and using WHO growth charts, will be listed by study time point as observed values and as changes from baseline. Change from baseline in anthropometric data will be tabulated as continuous data. In addition, the percentages of subjects who meet criteria for underweight, stunting, and wasting will be tabulated for each timepoint. Change and/or percent changes from baseline in AST, ALT, and serum ferritin will be tabulated for each evaluation timepoint. The proportion of subjects with abnormal hemoglobin at baseline who achieve transfusion-free hemoglobin normalization will be summarized, as will the proportion of subjects who maintain transfusion-free normal hemoglobin. The Denver II total score and functional area scores will be derived from the questionnaire in accordance with the Technical Manual and compared to appropriate demographic norms. The total score and functional area scores will be summarized as continuous data and according to the classification as to whether the subject displays abnormal/normal development. Shift tables will be used to tabulate dietary changes, including discontinuation of low-fat/low-cholesterol diet and/or introduction of an unrestricted age-appropriate diet. Observed values and changes and/or percent changes from baseline in other exploratory efficacy endpoints will be tabulated for each evaluation timepoint. **Exploratory Biomarkers** Exploratory biomarkers will be analyzed for the FAS. Potential diseaserelated biomarkers will be listed and observed values and changes and/or percent changes from baseline will be summarized by timepoint. Subgroup Analyses The impact of ADAs on safety, efficacy, PK, and PD endpoints will be explored descriptively. As subject numbers permit, other subgroup analyses of interest may be performed including, but are not limited to, age, gender, and race. **Measures to minimize** Local analgesic cream (e.g., eutectic mixture of local anesthetics) will be pain and distress (only allowed at least 20-30 minutes (or according to applicable institutional if specific for this guidelines) prior to IV placement or blood sampling. study)

Independent Safety Review Committee

Table of Contents

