8.1 General Considerations

All data will be presented in listings; summary tables and graphs will be provided, as appropriate. Unless otherwise noted, tabulations for efficacy endpoints will be presented for subjects in the Full Analysis Set (FAS). Descriptive summary statistics (n, mean, median, standard deviation, minimum and maximum) will be calculated for the continuous variables. Shift tables and/or frequencies and percentages will be produced for the categorical variables. When percentages are reported, the number of treated subjects will be used as the denominator, unless otherwise noted. As appropriate, 95% two-sided confidence intervals (CIs) will be calculated around the estimates based on the exact binomial distribution for binomial endpoints and the t-distribution for continuous endpoints.

Baseline will be defined as the last measurement prior to the first infusion of sebelipase alfa. (Note: For exploratory analyses, the first available measurement after initiation of treatment may be used as baseline if a pretreatment measurement is unavailable.) In order to facilitate comparison with literature, survival analyses will be presented with subject birth date as "time 0"; analyses of other endpoints over time will consider date of first dose as "time 0".

Details of the planned analyses and statistical methodologies will be provided in a separate Statistical Analysis Plan.

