8.7 Efficacy Analysis

Efficacy will be analyzed for the Full Analysis Set.

Survival will be analyzed as the proportion of subjects surviving to 12, 18, and 24 months of age. As a complementary analysis, Kaplan-Meier survival curves of survival since birth and survival since first dose of IMP will be presented. Median age at death will also be calculated. A Kaplan Meier estimate of median survival past first dose of IMP will be computed.

Estimated survival rates and median age at death derived from this study will be compared to rates/times reported in the literature, and will be discussed in conjunction with information derived from previous studies.

Anthropometric indicators of growth, standardized by age and gender in accordance with the methodology described by the WHO and using WHO growth charts will be listed by study time point as observed values and as changes from baseline. Change from baseline in anthropometric data will be provided as graphs, and also tabulated as continuous data. In addition, the percentages of subjects who meet criteria for underweight, stunting, and wasting will be tabulated for each timepoint.

Change and/or percent changes from baseline in AST, ALT, and serum ferritin will be presented graphically (and tabulated) for each evaluation timepoint.

A subject will be considered to have achieved transfusion-free hemoglobin normalization (TFHN) if the subject meets all of the following criteria:

- 1. Has two post-baseline measurements of hemoglobin at least 4 weeks apart that are both above the age-adjusted lower limit of normal (LLN)
- 2. Has no known additional measurements of hemoglobin that are below the age-adjusted LLN during the (minimum) 4-week period; and
- 3. Had no transfusions during the (minimum) 4-week period, and also no transfusions for 2 weeks prior to the first hemoglobin measurement in the (minimum) 4-week period

If all 3 criteria are met, the subject will be considered to have achieved TFHN on the date of the first hemoglobin assessment in the 4-week period. The proportion of subjects who achieve TFHN will be summarized and, if sufficient data are available, a summary of time to TFHN will be created.

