#### 7.2.3. Analyses for Laboratory Tests

Observed measurements and changes from Baseline to each study time point in clinical laboratory data will be summarized.

Frequencies of abnormal values relative to the laboratory normal range and clinically significant abnormal values as well as shift tables showing the change from baseline to post-baseline relative to the normal range will be summarized, if sufficient data are available for analysis.

Spaghetti plots for actual, change from baseline, and percent change from baseline will be created for the following parameters: ALT; AST; GGT; total bilirubin; albumin; alkaline phosphatase; total cholesterol; LDL-C; non-HDL-C; HDL-C; triglycerides; hemoglobin; platelets; prothrombin time (PT[INR]); partial thromboplastin time (PTT [INR]); and serum ferritin.

Plots of mean absolute change and mean percent change over time with standard deviations as error bars may be prepared for the following:

- Liver biochemical parameters: ALT/AST, GGT, bilirubin, albumin, alkaline phosphatase
- Lipids: total cholesterol, LDL-C, non-HDL-C, HDL-C, triglycerides
- Other: Hemoglobin, platelets, PT/PTT, serum ferritin
- The number of subjects contributing to each mean value will be presented in each figure

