# 7.3. Efficacy Analyses

Efficacy will be examined on the FAS. For the continuous endpoints, the observed values, change from baseline and percent change from baseline at each time of assessment will be summarized, and may include 95% confidence intervals (e.g. for time points with  $\geq 2$  observed data points).

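### The SAP drops the synopsis's baseline-anemia restriction on transfusion-free hemoglobin normalization, so a child who was never anemic counts as normalized

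*SAP*

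**What the plan says.** The protocol synopsis, under Efficacy, states: "The proportion of subjects with abnormal hemoglobin at baseline who achieve transfusion-free hemoglobin normalization will be summarized". It lists separately the proportion who maintain normal hemoglobin without transfusion.

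Protocol 8.7 and SAP 7.3.1.3 give identical operational definitions. A child achieves TFHN with two post-baseline hemoglobin values above the age-adjusted lower limit of normal (LLN) at least 4 weeks apart, no known low value between them, and no transfusion in that period or the 2 weeks before it. Both then say "The proportion of subjects who achieve TFHN will be summarized", with no baseline condition, and both add that "if sufficient data are available, a summary of time to TFHN will be created".

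Neither section states a denominator for TFHN. Protocol 8.1 supplies a default: "When percentages are reported, the number of treated subjects will be used as the denominator, unless otherwise noted". SAP 7.3 says "Efficacy will be examined on the FAS", and SAP 7 keeps subjects with missing data in percentage denominators. SAP 4.1, which lists departures from the protocol, does not mention TFHN.

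For the companion endpoint of maintained transfusion-free normal hemoglobin, both documents say that it applies "regardless of baseline hemoglobin value". That phrase is not attached to TFHN.

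**The concern.** The synopsis describes a recovery rate among children who had something to recover from. The definition in Protocol 8.7 and the SAP never looks at the baseline value, and the SAP is what will be programmed.

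Normalization of hemoglobin without transfusion is a named efficacy endpoint (SAP 5.2.1) under the hematological objective. The trial has no control arm, so readers will take the proportion as evidence of recovery on treatment. If children who were never anemic are counted as successes, the figure does not measure that. Any time-to-TFHN summary would also be pulled early, because such a child is dated at the first qualifying post-baseline sample.

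**Working it through.** **Can a child who is not anemic enroll?** Yes. In Protocol 4.3, severe anemia is one example in an open list of clinical concerns; an affected sibling is another. Protocol 3.2.2.1 notes that growth failure is not required and that treatment may start at a younger age than in LAL-CL03.

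**Does that child meet TFHN?** Suppose hemoglobin is never below the LLN and no transfusion is given. Two qualifying values at least 4 weeks apart exist, there is no low value between them, and there is no transfusion in the period or the 2 weeks before it. All three criteria are met.

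**Size.** The plan states no expected TFHN rate, so there is no figure to reproduce. Inputs:

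- N = 10, the maximum planned enrollment (Protocol 8.2, SAP 9.3).
- k = number normal at baseline who stay normal and untransfused (assumption; not in the documents).
- p = TFHN rate among the N − k anemic children (assumption; not in the documents).

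Unrestricted rate = [k + p(N − k)]/N. Restricted rate = p. Difference = (k/N)(1 − p).

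Difference in percentage points at N = 10 (p is treated as a rate, so some cells do not match whole numbers of children):

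| k | p = 0.75 | p = 0.5 | p = 0 |
|---|---|---|---|
| 1 | 2.5 | 5 | 10 |
| 2 | 5 | 10 | 20 |
| 4 | 10 | 20 | 40 |

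The difference is zero when k = 0 or p = 1.

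Whole-number examples with the SAP's exact (Clopper-Pearson) 95% intervals:

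| Case | Unrestricted (8.7 and SAP) | Restricted (synopsis) |
|---|---|---|
| k = 2, 6 of 8 anemic children respond | 8/10 = 80% (44.4 to 97.5) | 6/8 = 75% (34.9 to 96.8) |
| k = 4, 3 of 6 respond | 7/10 = 70% (34.8 to 93.3) | 3/6 = 50% (11.8 to 88.2) |
| k = 3, 0 of 7 respond | 3/10 = 30% (6.7 to 65.2) | 0/7 = 0% (0 to 41.0) |

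In the last row a normalization rate of 30% is printed although no child recovered.

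**Time to TFHN.** SAP 9.4.5 gives (days from first infusion + 1)/7 weeks. If a never-anemic child's first qualifying sample is at Week 1 (Day 7 ± 2, Appendix A), the time is (7 + 1)/7 = 1.14 weeks, ranging from (5 + 1)/7 = 0.86 to (9 + 1)/7 = 1.43. If it is at Week 2 (Day 14), the time is (14 + 1)/7 = 2.14 weeks. The SAP does not say how these times would be summarized.

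**The case against.** **The texts can be read together.** The synopsis gives a denominator and Protocol 8.7 gives a definition. The Protocol 8.1 default yields where another rule is noted, and the synopsis notes one. SAP 4.1 declares no change, which may mean none was intended. This is a fair account of the likely intent, and the baseline wording on the maintained endpoint supports it. But the restriction still appears nowhere in the SAP, neither in the TFHN proportion nor in the time-to-TFHN derivation, so a programmer working from the SAP would not apply it.

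**The bias need not be upward.** If only a fraction q of the children normal at baseline meet TFHN, the difference is (k/N)(q − p). With k = 2, one of the two staying normal and 6 of 8 anemic children responding, the unrestricted rate is 7/10 = 70% against 75%: 0.2 × (0.5 − 0.75) = −5 points. This stands as a limit on direction: the upward figures above hold for q = 1. In either direction, the printed rate mixes in children who had no anemia to recover from.

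**Much of it is visible anyway.** With about 10 children, subject listings and hemoglobin plots show who began normal. SAP 7.2.3 adds that "shift tables showing the change from baseline to post-baseline relative to the normal range will be summarized, if sufficient data are available for analysis". A reader could recompute the restricted rate. That limits the harm, but the shift tables ignore transfusions and none of these outputs corrects the printed proportion.

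**The restricted denominator has its own gap.** A child whose baseline value is normal only because of a recent transfusion would be dropped, although transfusion need is an example entry feature and criterion 3 already relies on transfusion records. This is a real cost, and the fix addresses it with a sensitivity summary.

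**Conclusion.** The concern holds. Two current parts of the protocol disagree on who belongs in the TFHN proportion. The SAP follows the unrestricted version without declaring a change, and under it a never-anemic, untransfused child counts as normalized.

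The size depends on how many children have normal baseline hemoglobin, which the documents do not give. For N = 10, and assuming those children stay normal and untransfused, the inflation is 2.5 to 20 points for one to four such children and response rates of 0.75 to 0.5 among the anemic children. With two such children and 6 of 8 responding, the gap is 5 points and the intervals largely overlap. The time effect arises only if the conditional summary is produced. No hypothesis test, error rate or decision rule is affected. This should be corrected before programming, but it does not threaten the trial's main conclusions.

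**What to change.** In Protocol 8.7 and SAP 7.3.1.3 and 9.4.5, restrict the TFHN proportion, and any time-to-TFHN summary, to FAS subjects with baseline hemoglobin below the age-adjusted LLN, and state that denominator. This matches the synopsis. Report children normal at baseline under the maintained endpoint, which already covers them.

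Optionally, flag children with a recorded transfusion in the 2 weeks before the baseline sample and add a sensitivity summary that includes them. The main denominator should not depend on whether such records exist.

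If the sponsor prefers the unrestricted proportion, the synopsis must be changed to agree and the denominator stated.

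The cost is a wording and denominator change. Hemoglobin is a mandatory Tier 1 test, so no new data are needed. The descriptive interval widens: 61.9 points for 6/8 against 53.1 for 8/10, and 76.4 for 3/6 against about 59 for 7/10. A child whose baseline value is normal only after a recent transfusion leaves the main denominator; the sensitivity summary shows the effect where records exist.

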# 7. STATISTICAL ANALYSIS

The Alexion Biostatistics Department or designee will perform the statistical analysis of the data derived from this trial. The analysis will be performed using the SAS® Life Science Analytics Framework version 4.7.2 or higher.

No formal inferential statistical testing will be performed. As appropriate, 95% two-sided confidence intervals (CIs) will be calculated around the estimates based on the exact binomial distribution (Clopper-Pearson method) for binomial endpoints and the t-distribution for continuous endpoints. Confidence intervals, where presented, will be considered descriptive and will be provided to facilitate clinical review and interpretation.

All data collected in this study will be provided in subject data listings sorted by subject number; the dose of SBC-102 temporally associated with the data will be included on the listing. Summary tables and/or graphs will be presented for each endpoint, as appropriate to the data, by evaluation time point.

Unless otherwise noted, the following standard conventions will be used for creating descriptive summaries:

- Continuous numeric endpoints will be summarized by providing the number of subjects with non-missing data, the mean and standard deviation (SD) of the data, and the minimum, first quartile (Q1), median, third quartile (Q3), and maximum value. Mean, median values, Q1 and Q3 will be presented with one decimal point more than the original value, SD will be displayed with two decimal points more than the original value will have the same number of decimal points as the original value;
- For categorical endpoints, the number and percentage of subjects with each possible outcome will be displayed. The denominator for percentages will include subjects with missing data.

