#### 7.3.1. Handling of Dropouts or Missing Data

All data will be analyzed as they were collected in the database. Missing data in general will not be imputed, any imputation techniques, if applied, are described in Section 9.

Proprietary and Confidential 30

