#### 9.4.2 Time to Death (from Birth)

Time to Death (months) = [(Date of Death - Date of Birth + 1)/365.25]\*12;

This derived variable will be used in the calculation of Kaplan-Meier estimate of median age at death/median survival since birth. This calculation will be adjusted for subjects born prematurely; details are described in Section 7.3.1.4.

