#### 9.4.3 Time to Death (from first Infusion of SBC-102)

Time to Death (months) = [(Date of Death - Date of First SBC-102 Infusion + 1)/365.25]\*12;

This derived variable will be used in the calculation of Kaplan-Meier estimate of median survival since first dose of SBC-102.

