#### 9.4.5 Time to Transfusion-Free Hemoglobin Normalization

Time to Transfusion-Free Hemoglobin (Weeks) = (Date of First Assessment in 4 week period where conditions for TFHN are satisfied\* - Date of First SBC-102 Infusion + 1)/7;

\*See Section 7.3.1.3 for details.

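### The SAP names no method for time to transfusion-free hemoglobin normalization, and its default summary would cover achievers only and lean toward fast response.

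*SAP*

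**What the plan says.** Hemoglobin normalization without transfusion is among the secondary efficacy endpoints in SAP 5.2.1. SAP 7.3.1.3 defines TFHN by two normal values at least 4 weeks apart plus transfusion conditions, and plans the proportion who achieve it. On timing it says only that "if sufficient data are available, a summary of time to TFHN will be created". Protocol 8.7 says the same and adds no method.

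SAP 9.4.5 derives the time from the "Date of First Assessment in 4 week period where conditions for TFHN are satisfied", counted in weeks from the first infusion. A child who never meets the conditions has no such date.

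SAP Section 7 sets the fallback: "Unless otherwise noted, the following standard conventions will be used for creating descriptive summaries". The first of these is that "Continuous numeric endpoints will be summarized by providing the number of subjects with non-missing data", followed by mean, SD, quartiles, median and range. On missing values, SAP 7.3.1 says: "Missing data in general will not be imputed, any imputation techniques, if applied, are described in Section 9". Section 9 contains no rule for time to TFHN.

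The three preceding time variables are treated differently. For 9.4.2: "This derived variable will be used in the calculation of Kaplan-Meier estimate of median age at death/median survival since birth". For 9.4.3: "This derived variable will be used in the calculation of Kaplan-Meier estimate of median survival since first dose of SBC-102". Section 9.4.4 likewise links time to peak antibody titer to a Kaplan-Meier median. Section 9.4.5 has no such sentence.

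**The concern.** A programmer who follows the SAP finds a variable that is non-missing only for achievers, no named estimator, no imputation, and a default that summarizes non-missing values. The result is a mean and median time among achievers.

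That figure conditions on success. A child who dies at week 5, withdraws, or stays anemic throughout contributes nothing to it, and slow responders are the most likely to be lost before they respond. The printed median therefore tends to be shorter than the time by which half of the treated children respond. It can also be printed when fewer than half ever respond.

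The setting makes this foreseeable. Protocol 1.1.1 describes untreated disease as usually fatal within the first 6 months of life, TFHN needs at least 4 weeks of observation to confirm, and enrollment is capped at 10, so each lost child can move the median. A reader of the report would probably take the number as time to response in treated infants.

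**Working it through.** The documents state no TFHN rate, time or death rate, so there is no planned figure to reproduce. All rates below are assumptions, used only to show direction and possible size.

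**1. Constant hazards.** Let h1 be the weekly hazard of TFHN and h2 the weekly hazard of leaving without TFHN, with every exit treated as death.

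- Among achievers, the time to TFHN is exponential with rate h1 + h2, so the achievers' median is ln 2 / (h1 + h2).
- Among all treated, the cumulative incidence is F(t) = [h1 / (h1 + h2)] × [1 − exp(−(h1 + h2)t)]. The 50% time solves F(t) = 0.5 and exists only if h1 > h2.

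Central case, h1 = 0.03 and h2 = 0.02:

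- Achievers: ln 2 / 0.05 = 13.9 weeks.
- All treated: 0.5 = 0.6 × [1 − exp(−0.05t)], so exp(−0.05t) = 1/6 and t = ln 6 / 0.05 = 35.8 weeks.

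Corners of h1 = 0.02 to 0.05 and h2 = 0.01 to 0.02:

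| h1 | h2 | Achievers' median (weeks) | 50% time, all treated (weeks) |
|---|---|---|---|
| 0.02 | 0.01 | ln 2 / 0.03 = 23.1 | ln 4 / 0.03 = 46.2 |
| 0.02 | 0.02 | ln 2 / 0.04 = 17.3 | not reached (ceiling is 50%) |
| 0.05 | 0.01 | ln 2 / 0.06 = 11.6 | ln 2.5 / 0.06 = 15.3 |
| 0.05 | 0.02 | ln 2 / 0.07 = 9.9 | ln(1/0.3) / 0.07 = 17.2 |

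So the achievers' median is 9.9 to 23.1 weeks, against 15.3 weeks to not reached.

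If every exit were instead an uninformative withdrawal, and so censored, the comparison in the central case would be ln 2 / 0.03 = 23.1 weeks. The achievers' 13.9 weeks is still too short.

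**2. Trials of 10 children (20,000 simulations per setting).** Time to TFHN is exponential with an assumed latent median; deaths fall uniformly over weeks 0 to 26; follow-up is 144 weeks. Entries are the typical achievers' median against the typical all-treated median, in weeks.

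| Latent median | No deaths | 10% die | 40% die |
|---|---|---|---|
| 12 | 12.1 vs 12.1 | 11.6 vs 12.6 | 9.7 vs 14.4 |
| 24 | 23.7 vs 24.2 | 22.6 vs 26.0 | 18.5 vs 36.4 |
| 48 | 40.2 vs 48.8 | 39.3 vs 54.2 | 33.9 vs 94.0 |

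The gap vanishes when response is fast and nobody dies. It grows with mortality and with slow response.

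**3. Choice of estimator.** Take 10 treated children: TFHN at weeks 4, 6, 8, 12, 20 and 36; deaths without TFHN at weeks 2, 5 and 9; one living non-achiever followed to week 144.

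- Default on the 6 achievers: median (8 + 12)/2 = 10.0 weeks; mean 86/6 = 14.3 weeks.
- Cumulative incidence with death competing: nobody is censored before the last event, so each achiever adds 1/10. It reaches 50% at week 20 and ends at 60%.
- One minus Kaplan-Meier with deaths censored: the risk sets at the six TFHN times are 9, 7, 6, 4, 3 and 2. At week 12 it is 1 − (8/9)(6/7)(5/6)(3/4) = 52%. After the factors 2/3 and 1/2 it ends at 84%, although only 60% achieved TFHN.

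Adding Kaplan-Meier in the style of 9.4.2 to 9.4.4 would therefore help with living non-achievers but would not handle deaths properly.

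**The case against.** The strongest reply is that the SAP never says mean or median among achievers. It promises an unspecified summary, only if data suffice, and Section 7 also says displays will be chosen as appropriate to the data. A statistician could choose a time-to-event method without breaching the plan. This stands as a limit: the achievers-only reading is inferred from the default and from the absence of any alternative.

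A reader might infer that the missing censoring date in 9.4.5 by itself proves that non-achievers are excluded. It does not. Sections 9.4.2 and 9.4.3 also define a time only for children with the event and give no censoring date, yet SAP 7.3.1.1 plans Kaplan-Meier with a count of censored children. What separates 9.4.5 is that no such estimate is named for it anywhere.

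A reader might also infer that deaths and non-responders vanish from the hemoglobin endpoint. The documents do not support that. The TFHN proportion is reported alongside, with a percentage denominator that keeps subjects with missing data; the default summary prints its n; and with at most 10 children, listings and individual hemoglobin plots are planned. A reader would see, for example, 6 of 10 beside n = 6. This shows that selection occurred, but it does not correct the median.

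Finally, the central example implies that 0.02/0.05 = 40% of children exit without TFHN, and it counts every exit as death. The documents give no such rate and expect at least 18 months of treatment. That limits the size of the claim but not its direction.

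**Conclusion.** The point holds as a gap in method with a foreseeable consequence. Time to TFHN has no named estimator, and the Section 7 default would produce an achievers-only mean and median. That summary is biased toward faster response whenever children die, withdraw or never normalize.

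The size is conditional on assumed rates. It is 13.9 against 35.8 weeks at hazards of 0.03 and 0.02; over the wider range it is 9.9 to 23.1 weeks against 15.3 weeks to not reached; and it is close to nothing if almost all children achieve TFHN early. It would go too far to say that the plan will report a misleadingly fast response, because neither the method nor the rates are settled in the documents.

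Severity is minor to moderate. The summary is descriptive, untested and conditional on sufficient data, and the endpoint itself is carried by the proportion.

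**What to change.** In SAP 7.3.1.3 and 9.4.5, state that:

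- Time to TFHN is shown as a cumulative incidence curve for the same children as the TFHN proportion. Name that group explicitly: either all FAS children, or those with abnormal baseline hemoglobin. The protocol synopsis restricts the normalization proportion to the latter, while SAP 7.3.1.3 has no such limit, so a child normal at baseline could count as an early achiever.
- Death before TFHN is a competing event.
- Living non-achievers, including those who withdraw, are censored at the last hemoglobin assessment.
- The time at which 50% is reached is given only if it is reached.
- Any achievers-only summary is labeled as such and shown with the number of achievers out of the number in the group.

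The cost is SAP wording and one figure. No new data are needed.
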